In this study, we will evaluate the efficacy and safety of atorvastatin in SCD patients. At the completion of this trial, we will have an improved understanding of the contribution of endothelial dysfunction and soluble fms-like tyrosine kinase (sFLT-1) to the pathophysiology of albuminuria in SCD. If the data support the hypothesis that atorvastatin is safe and effective in this population, we plan on carrying out adequately powered studies to more definitively evaluate its safety and efficacy in the treatment and/or prevention of albuminuria in SCD.

Intervention: We will conduct a randomized, double-blind, placebo-controlled, crossover trial of atorvastatin (n = 19). Subjects will receive atorvastatin 40 mg/day or placebo for 6 weeks, separated by a 4 week washout phase. At the end of the washout period, a repeat history and examination and laboratory studies will be performed which will serve as a baseline for the second treatment phase, and patients will receive either atorvastatin or placebo, depending on their first treatment administration.

IND Holder: EXEMPT

Specific Aims:

- A) To evaluate the effect of atorvastatin on endothelial dysfunction, assessed using ultrasound imaging of the brachial artery, in sickle cell disease patients.
- B) To evaluate the effect of atorvastatin on plasma markers of endothelial activation, plasma levels of sFLT-1 and VEGF, heme oxygenase activity, rho/rho kinase activity, and TF-mediated sFLT-1 release from monocytes in sickle cell disease patients.
- C) To evaluate the effect of atorvastatin on albuminuria and estimated glomerular filtration rate in sickle cell disease patients
- D) To evaluate the association of endothelial dysfunction with pulmonary arterial pressure.

Hypotheses/Estimates: Our primary hypothesis is that endothelial dysfunction is an important contributor to the pathophysiology of albuminuria in SCD. We propose that atorvastatin will

Title of the Protocol: The effect of atorvastatin on endothelial dysfunction and albuminuria in sickle cell disease

improve endothelial dysfunction, decrease levels of sFLT-1, and decrease albuminuria in SCD patients.

Criteria for Evaluation:

Efficacy: Primary Endpoint: *Endothelial Dysfunction:* This will be assessed non-invasively using a brachial artery shear stress method. Assessments will be obtained at Baseline, and then at week 6 during the Treatment Phase. The primary efficacy measure will be a comparison of the % change in FMD from baseline to week 6.

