Endothelial Dysfunction – Vascular endothelial dysfunction will be assessed by measuring endothelium-dependent (flow-mediated) and endothelium-independent (nitroglycerin-mediated) dilation of the brachial artery as described previously (90,91). This technique has been safely performed in SCD patients (92,93). Subjects will be asked to hold all morning medications on days they have study visits until after the brachial ultrasound test. The reason for this is to avoid any effects of vasoactive medications. They are also required to refrain from smoking, vigorous exercise, caffeine, and eating and drinking (except water) for at least 6 hours before the brachial ultrasound procedure is scheduled. (Revised 06/03/2013.) Ultrasound images of the right brachial artery proximal to the antecubital fossa will be acquired using a 12 MHz linear-array transducer. The first set of baseline images will be obtained after 10 minutes of supine rest. Reactive hyperemia will be induced by inflating a pneumatic occlusion cuff placed around the upper forearm to a suprasystolic pressure (~ 200 mmHg) for 5 minutes, and then deflating the cuff. Images of the artery will be recorded for two minutes after cuff deflation. After 10 minutes of rest, a second set of baseline images will be acquired. Sublingual nitroglycerin (0.4 mg) will then be administered with acquisition of ultrasound images for the subsequent 5 minutes.

Gated end-diastolic images will be stored in a digital format on a personal computer for subsequent offline quantification. Each set of recordings will be coded and analyzed in random order by a blinded observer. Measurements will be performed using customized software (Brachial Tools, Medical Imaging Applications, LLC). Arterial diameter will be measured from the lumen-intimal interfaces of the proximal and distal arterial walls. Data from at least ten end-diastolic frames will be averaged for each baseline measurement and from at least three frames at maximum dilation during reactive hyperemia and following administration of nitroglycerin. FMD will be calculated as the % change in arterial diameter in response to reactive hyperemia, and NTMD will be quantified as the % diameter change following administration of nitroglycerin.

Assessments will be obtained at Baseline, Week 4 and Week 6 during each Treatment Phase. The primary efficacy measure will be a comparison of the % change in FMD from baseline to week 6. NTMD is a secondary efficacy measure.

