Statistical analysis strategy: Descriptive statistics of endothelial dysfunction measures (FMD%, NTMD%), soluble VCAM, soluble ICAM, sFLT-1, VEGF, heme oxygenase activity and rho/rho kinase activity will be presented by treatment and by visit, along with corresponding charts. FMD% and NTMD% will be log-transformed. To evaluate the effect of atorvastatin on endothelial dysfunction measures, we will perform a comparison of treatment by visit, using Student t-test subsequently followed by crossover ANOVA model testing carry-over effect and treatment effect. For soluble VCAM, soluble ICAM, sFLT-1, VEGF, heme oxygenase activity and rho/rho kinase activity, since they are not normally distributed, we will compare atorvastatin with placebo using Wilcoxon sign rank test. Similar analysis will be performed for the albuminuria and estimated GFR values. In addition, the relationship between outcome measures and treatment will be studied through a multiple regression analysis.

To evaluate the effect of atorvastatin on albuminuria, we will examine albuminuria both as a continuous variable using a linear mixed model to analyze the effect and as a categorical variable using a generalized estimating equation approach. Point estimates and confidence interval for the effect of albuminuria will be presented. Distribution of any complication among patients by treatment will be presented. The association of side effects by treatment will be tested using McNemar's test.

Differences in pre- and post- treatment echocardiographically-defined TRV will be described in tabular and graphical terms. (Added 06/04/2013.)

Sample Size Justification: Based on previous literature (70), we assume a standard deviation of 0.894 for changes in mean FMD%. In a 2x2 crossover design, the minimum required sample size is 9 per sequence to detect a clinically meaningful difference of 0.65 in mean changes in FMD% between atorvastatin and placebo groups at significance level $\alpha = 0.05$ with 80% power. Assuming a 5% attrition rate, we will enroll 19 patients for this study. (Revised 06/03/2013.)

Anticipated Outcomes: We anticipate that atorvastatin, by improving endothelial dysfunction, will decrease albuminuria in SCD. Furthermore, atorvastin will increase HO activity, but decrease rho kinase activity, sFLT-1 levels and TF-mediated sFLT-1 release from monocytes.

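### Cheap improvement: state how baseline FMD enters the primary crossover analysis, and adjust for the Day 0 period difference rather than subtract it

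*Combined protocol and SAP*

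**What the plan says.** The synopsis (Criteria for Evaluation) and the Endothelial Dysfunction part of Assessments give the same primary measure: "The primary efficacy measure will be a comparison of the % change in FMD from baseline to week 6". On timing, Assessments says: "Assessments will be obtained at Baseline, Week 4 and Week 6 during each Treatment Phase". The synopsis makes the end-of-washout evaluation the baseline for the second treatment phase, and the schedule of assessments marks a brachial ultrasound at Day 0 of both phases. Each period therefore has its own FMD baseline.

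Statistical Methods says "FMD% and NTMD% will be log-transformed", and then: "we will perform a comparison of treatment by visit, using Student t-test subsequently followed by crossover ANOVA model testing carry-over effect and treatment effect". It names no baseline FMD covariate. It adds that "the relationship between outcome measures and treatment will be studied through a multiple regression analysis", without listing covariates. Potential Pitfalls says that analyses will be adjusted for hydroxyurea.

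Sample Size Justification says "we assume a standard deviation of 0.894 for changes in mean FMD"% and "the minimum required sample size is 9 per sequence to detect a clinically meaningful difference of 0.65 in mean changes in FMD"%, at 5% significance and 80% power. Nineteen patients are to be enrolled to allow for 5% attrition.

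**The concern.** In a crossover each patient is already their own control. Subtracting a separate baseline reading in each period brings in the noise of two more scans. That helps only if the Day 0 and week-6 period differences move closely together. If they do not, the subtraction costs precision that the same scans could supply through a covariate.

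The text is also open on what is analysed. The primary measure and the sample size point to changes. A treatment comparison made visit by visit could equally be an unadjusted week-6 comparison. These two analyses can have very different power, and the plan does not choose.

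The stake is the precision of the FMD effect from about 18 completers. Potential Pitfalls says the estimates from this exploratory trial will be used to design and size a definitive study.

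**Working it through.** **Inputs from the documents.** Difference 0.65; SD 0.894; 9 per sequence (N = 18); significance level 0.05, taken as two-sided because that reproduces the stated size.

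**Assumed, not in the documents.** The correlation c between a patient's period 1 minus period 2 difference at Day 0 and at week 6; the ratio of the SDs of those two differences (equal at first); no carry-over at first. All power figures are on the 0.65/0.894 scale, not on a log scale.

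**1. The plan's own figure.** Take 0.894 as the SD of the within-patient difference of changes. The noncentrality is 0.65/(0.894/√18) = 0.65/0.2107 = 3.085 on 16 degrees of freedom, which gives 82.5% power. Eight per sequence gives 77.2%, so 9 is the minimum. Enrolment is 18/0.95 = 18.9, rounded up to 19. The size reproduces.

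**2. Variances.** Let V be the variance of each period difference.

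- Change score: V + V − 2cV = 2V(1 − c)
- Adjusted for the Day 0 difference: V(1 − c²)
- Adjusted relative to change score: (1 − c²)/[2(1 − c)] = (1 + c)/2
- Unadjusted week 6: V

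Before the slope is estimated, the adjusted variance never exceeds either alternative. Estimating the slope from 18 patients raises the variance on average by the factor 1 + 1/14 = 1.071 and costs one degree of freedom (16 to 15). On variance alone, break-even with change scores is at (1 + c)/2 = 14/15, so c = 0.87. The lost degree of freedom brings break-even in power to about c = 0.85.

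**3. Power**, holding the SD of the change contrast at 0.894 (simulation, 100,000 trials per value, slope estimated):

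| c (assumed) | Change score | Adjusted | Unadjusted week 6 |
|---|---|---|---|
| 0 | 82.5% | 97.5% | 98% |
| 0.25 | 82.5% | 94% | 94% |
| 0.5 | 82.5% | 89% | 82.5% |
| 0.7 | 82.5% | 85.5% | 61% |
| 0.9 | 82.5% | 81.6% | 25% |
| 0.99 | 82.5% | 80% | 7% |

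**4. Unequal variances.** If the Day 0 SD is k times the week-6 SD, the ratio in step 2 becomes (1 − c²)/(1 + k² − 2kc).

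- k = 0.7: the ratio is 0.67, 0.95 and 1.00 at c = 0, 0.5 and 0.7. Adjusted power is about 92%, 82% and 80%.
- k = 1.4: the ratio is 0.34, 0.48 and 0.51 at the same values. The gain is about 15 to 17 points.

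**5. Carry-over.** Assume an amount L = 0.3 after atorvastatin given first, with a true effect of 0.65 and equal variances.

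- Persisting through period 2: the change-score bias is 0. The adjusted bias is −L(1 − c)/2, so the estimate averages 0.50 at c = 0 and 0.575 at c = 0.5. Adjusted power is then about 83.5% and 80%.
- Confined to the period-2 baseline: the change-score bias is +L/2, an average of 0.80. The adjusted bias is +cL/2, an average of 0.65 at c = 0 and 0.725 at c = 0.5.

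Root-mean-square error, adjusted against change score: 0.219 against 0.211 (c = 0) and 0.206 against 0.211 (c = 0.5) in the first case; 0.160 against 0.259 and 0.207 against 0.259 in the second. Comparing Day 0 differences between sequences would detect a carry-over of 0.3 in only about 16% of trials at c = 0 and 6% at c = 0.9.

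**The case against.** The strongest case against is that this is a preference between valid analyses. The primary measure and the sample size are both change-based, so on that reading the plan is consistent. The benefit rests on two quantities the documents do not give, and it can be negative. With k = 0.7 and c = 0.5, adjusted power is about 82%, so the gain is gone. If carry-over persists through period 2, the adjusted estimate is biased and change scores are not; the plan's own carry-over test shows that the investigators think carry-over possible. Finally, the power figures are on the sample-size scale, while the planned analysis is on logs.

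All of this stands as a limit on the size of the gain and as a reason to keep change scores as a sensitivity analysis. It does not remove the specification gap. Nor does the carry-over argument settle the choice, because carry-over confined to the period-2 baseline biases change scores more.

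Three stronger readings are tempting and are not supported:

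- A reader might infer that the change-score analysis, or the sample size, is wrong. The contrast is valid and the 9 per sequence reproduces. If 0.894 were the SD of one period's change and the two changes were uncorrelated, power would be 53.6%. The wording leaves that open, but that reading does not reproduce the plan's figure, so it is a matter for clarification.
- A reader might expect 15 points. That is the equal-variance value at c = 0 only.
- A reader might think that the hydroxyurea adjustment or the multiple regression already deals with baseline FMD. Hydroxyurea is a different variable, and the regression lists no covariates. It could include baseline FMD, but nothing says that it does.

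**Conclusion.** This is a cheap improvement and a request for specification, not an error. The documents establish that the primary contrast is a change from each period's baseline, that Day 0 scans exist in both periods, and that neither the ANOVA response nor a baseline FMD term is specified.

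With 9 per sequence, equal variances and no carry-over, adjustment moves power from 82.5% to between about 97.5% (c = 0) and 80% (c = 0.99), crossing over near c = 0.85. A smaller Day 0 variance shrinks the benefit or removes it over much of the range of c; a larger one increases it. Under equal variances and no carry-over, the adjusted model stays within about 3 points of the better of the two unadjusted readings. Those two readings differ from each other by about 57 points at c = 0.9 (82.5% against 25%). That robustness to an unknown c is the better argument for the change, more so than any single gain. Confidence is moderate, because neither c nor the variance ratio is known.

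**What to change.** (a) Make the primary analysis a regression of the period 1 minus period 2 difference in log week-6 FMD% on sequence (which carries the treatment effect, with the intercept carrying the period effect) and on the same difference in log Day 0 FMD%. Define baseline as Day 0 of each period, or the consolidated Screening/Day 0 visit where that option is used. Say whether the hydroxyurea adjustment in Potential Pitfalls enters this model or a secondary one.

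(b) Pre-specify the change-score analysis as the sensitivity analysis. Report the Day 0 difference between sequences as a carry-over estimate with a confidence interval, and do not use it as a gate for choosing the analysis.

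(c) Clarify four items: which quantity has SD 0.894 (and, if it is one period's change, the assumed correlation between a patient's two changes); the scale on which 0.65 and 0.894 apply, given the log transformation; how FMD% readings at or below zero are handled; and the covariates and status of the multiple regression.

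The cost is wording only, with no extra patients, visits or scans. The statistical price is one residual degree of freedom plus slope estimation, at most about 3 power points, and bias if carry-over persists through period 2. The sensitivity analysis in (b) is there to expose that bias.

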With the evidence of chronic inflammation and endothelial dysfunction in SCD, and the ability of statins to decrease inflammation following hypoxia-reoxygenation injury and improve endothelial dysfunction, we propose that atorvastatin will have a beneficial role in patients with SCD.

PRELIMINARY DATA

Nephropathy is Associated with Vasculopathic Complications in Sickle Cell Disease: We have previously

shown that PHT, diagnosed using Doppler echocardiography is associated with nephropathy ($p = 0.01$) in SCD patients (9). Serum creatinine (1.1 ± 0.5 mg/dL vs. 0.8 ± 0.3 mg/dL, $p = 0.02$) and blood urea nitrogen (16.1 ± 11.7 mg/dL vs. 10.1 ± 6.6 mg/dL, $p = 0.01$) were higher in patients with PHT compared to those without PHT. We have recently confirmed the high prevalence of albuminuria (assessed by spot urine measurements of microalbumin/creatinine ratio) in SCD (Figure 1). In a cross-sectional study of 73 SCD patients, normoalbuminuria (urine albumin excretion [UAE] < 30 mg/g creatinine) was observed in 34 patients (46.6%), microalbuminuria (UAE: 30 – 299 mg/g creatinine) in 24 patients (32.9%) and macroalbuminuria (UAE: ≥ 300 mg/g creatinine) in 15 patients (20.5%) (12). Albuminuria was correlated with age ($r = 0.32$, 95% CI: 0.09–0.51; $p = 0.006$). As expected, albuminuria was inversely correlated

[figure not shown]

Figure 1: The Prevalence of Albuminuria in SCD

with estimated GFR (MDRD method) ($r = -0.24$; $p = 0.04$) and positively correlated with cystatin C ($r = 0.25$; $p = 0.03$). We also observed significant associations between albuminuria and both echocardiography-defined

PHT ($p = 0.04$) and a history of stroke ($p = 0.002$). In patients with measurable tricuspid regurgitant jet velocities (TRV), the TRV was significantly higher in those with macroalbuminuria compared to patients with microalbuminuria and normoalbuminuria (3.15 m/s vs. 2.45 m/s vs. 2.45 m/s; $p = 0.00068$). We were unable to detect significant associations between albuminuria and the number of acute pain episodes, history of acute chest syndrome, history of leg ulcers, history of priapism or retinopathy.

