
An Investigational New Drug (IND) application to support the administration of atorvastatin to SCD patients is pending. (**FDA determined study to be EXEMPT from IND. Letter on file.**)

Inclusion Criteria:

- a) HbSS or HbS β^0 thalassemia between ages of 18 and 70; (**Maximum age revised 06/03/2013 and 04/07/2015.**)
- b) albuminuria (micro- or macroalbuminuria, defined as ≥ 30 mg/g creatinine);
- c) serum ALT ≤ 2 times upper limits of normal and/or GGT (**added 05/12/2015, revised 06/13/2017**) ≤ 3 times upper limits of normal;
- d) platelet count $\geq 150,000$ cu/mm;
- e) normal baseline coagulation profile (PT/INR, PTT);
- f) non-crisis, steady state with no severe pain episodes during the preceding 4 weeks, and no documented infection in the 2 weeks prior to enrollment; (**infection added 8/26/11**)
- g) ability to understand the requirements of the study;
- h) if a woman of childbearing potential, must use an adequate method of contraception; and
- i) if receiving hydroxyurea, ACE inhibitors or ARBs, should be on a stable dose for at least 3 months.

Exclusion Criteria:

- a) hypersensitivity to any component of atorvastatin, **or history of adverse reaction to statins;** (**ADDED 8/26/2011**)
- b) pregnant or breastfeeding;
- c) on statin therapy;
- d) history of metastatic cancer;
- e) current history of alcohol abuse;
- f) history of diabetes mellitus or poorly controlled systemic hypertension;
- g) end-stage renal disease;
- h) total cholesterol level < 80 mg/dL and LDL cholesterol > 130 mg/dL;
- i) on a chronic transfusion program;
- j) ingested any investigational drugs within the past 4 weeks;
- k) prior history of any myopathy;
- l) allergy to nitroglycerin;
- m) *taking any of the following drugs: phosphodiesterase-5 inhibitors (e.g., sildenafil), CYP3A4 inhibitors (e.g., cyclosporine, protease inhibitors), macrolide antibiotics (e.g., clarithromycin, erythromycin), fibric acid derivatives (e.g. gemfibrozil), niacin, colchicines, antifungal agents (azole derivatives), amiodarone, danazol, daptomycin, diltiazem, verapamil, eltrombopag, everolimus, fosphenytoin, or lanthanum.*

Patients will also be encouraged to avoid grape fruit juice and red yeast rice for the duration of the study.

Atorvastatin is contraindicated during pregnancy and breast-feeding. (Added 08/26/2011.)

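### Albuminuria category is to be analysed by GEE in 18–19 patients with no small-sample method, so its error rate, and whether it can be fitted at all, depend on choices the plan leaves open

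*Combined protocol and SAP*

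**What the plan says.** Under Statistical Methods, Statistical analysis strategy, albuminuria is to be analysed as a continuous variable by a linear mixed model "and as a categorical variable using a generalized estimating equation approach". Of these models the plan says "Point estimates and confidence interval for the effect of albuminuria will be presented". A Wilcoxon signed-rank comparison of albuminuria is also planned. For the GEE the section gives no category definition, link, working correlation, choice of visits, variance estimator, small-sample correction or action if the model does not fit.

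The visits are not settled elsewhere either. The synopsis (Secondary Endpoints, Renal Function) lists baseline and week 6. The Assessments section lists baseline, week 4 and week 6 of both periods.

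The trial is sized on flow-mediated dilation (FMD) only: "the minimum required sample size is 9 per sequence", and "Assuming a 5% attrition rate, we will enroll 19 patients for this study". Inclusion criterion b) requires "albuminuria (micro- or macroalbuminuria, defined as" at least 30 mg/g creatinine, so every patient enters in the micro or macro category.

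**The concern.** The usual GEE standard error is a sandwich estimate that is justified when there are many independent clusters. Here the clusters are patients, and there are 18 or 19. Category is also likely to be nearly constant within a patient. The Preliminary Data describe a very wide spread between patients, so most sit far from 30 and from 300 mg/g and would not cross either cut between periods. Because everyone enters at or above 30, being below 30 is the rarer state.

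With so few changers, the robust Wald statistic can be erratic and some fits separate. Albuminuria is in the trial's title and in Aim C, and the results are meant to guide larger studies. An unreliable category result, or a model chosen only after the planned one fails, would carry forward into those studies.

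**Working it through.** **1. The plan's own figure.** The documents state no error rate or expected number of category changes, so the figure to reproduce is the FMD sample size. Reading 0.894 as the SD of the within-patient difference, with a two-sided 5% test and df = n − 2, the noncentrality at n = 18 is 0.65 × √18 / 0.894 = 3.08. Power is 82.5% (80.0% at n = 17), so 9 per sequence reproduces. Then 18 / 0.95 = 18.9, so 19 are enrolled. About 18 clusters is therefore the right basis.

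**2. Spread between patients (Preliminary Data, 73 patients: 34 / 24 / 15).** Below 30: 34/73 = 0.466, z = −0.086. Below 300: 58/73 = 0.795, z = 0.822. On the log10 scale the cuts are 1 unit apart, so SD = 1 / (0.822 + 0.086) = 1.10. The mean is 1.477 + 0.086 × 1.10 = 1.57, a median of about 37 mg/g. In natural logs the SD is about 2.53.

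**3. Expected changers.** Patients enter if a screening value is at least 30, and week-6 category is then compared between treatments with no drug effect. The within-patient SD is an assumption, taken from 0.05 to 0.40 log10. Expected discordant patients of 18: under 0.5 up to 2.8 at the 30 cut, 0.5 to 3.8 at the 300 cut, and 0.8 to 6.4 over all three categories.

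**4. Week 6 only.** With b and c patients changing in each direction, the unadjusted robust Wald statistic for a paired difference in proportions is (b − c)² / [(b + c) − (b − c)²/n]. At n = 18:

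- 2–0: 4 / (2 − 4/18) = 2.25
- 3–0: 9 / (3 − 9/18) = 3.60
- 4–0: 16 / (4 − 16/18) = 5.14

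The critical value is 3.84, so this test cannot reject with 2 or 3 discordant patients. With exactly 4 it rejects only at 4–0 or 0–4, that is 2/16 = 12.5%. Enumerating a logistic GEE (independence, with and without period) gave about 1–4% where 2–3 discordant patients are expected, and at most 7.3% over the grid. Simulated exchangeable GEE gave 1–7%, with 2–51% of fits not estimable.

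**5. Weeks 4 and 6 modelled.** Setting: 18 patients, logistic GEE with treatment and period, exchangeable correlation, robust Wald, no drug effect, within-patient SD 0.5 or 0.8 in natural logs (0.22 or 0.35 log10). Rejection at nominal 5%:

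| Cut | SD | 1,200 runs | 800 runs | 500 runs |
|---|---|---|---|---|
| 30 | 0.5 | 14.7% | 12.0% | about 17% |
| 30 | 0.8 | 9.0% | 9.4% | about 11% |
| 300 | 0.5 | 5.3% | 6.2% | about 5–6% |
| 300 | 0.8 | 8.0% | 7.6% | about 5–6% |

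The 800- and 500-run columns are per usable fit. How failed fits were counted in the 1,200-run column is not recorded. In the 500-run set the 30-cut rates are 13% and 10% of all runs. Fits failed in 20–21% (SD 0.5) and 5% (SD 0.8) of runs at the 30 cut. Independence correlation gave 11.9% and 8.6% at 30, and 4.2% and 6.9% at 300. A wider set of repeated-visit models (600 trials each; SD 0.15–0.40 log10, some with hydroxyurea or the baseline visit) gave 7–14% at 30 and 2–10% at 300. Its worst case was 13.8% of usable fits with 19% failing: 13.8 × 0.81 = 11.2% of all trials.

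**6. Alternatives.** Exact McNemar with all changes in one direction: 2 × 0.5⁵ = 0.0625 with 5 discordant and 2 × 0.5⁶ = 0.031 with 6, so at least 6 are needed. Sequence-stratified exact Mainland–Gart: the smallest p with 6 discordant is 1/C(6,2) = 0.067, and with 7 it is 1/C(7,3) = 0.029, so at least 7. In the setting of step 5, a Mancl–DeRouen variance with t on 16 df gave 2.1% and 3.0% at the 300 cut, but 8.9% and 4.1% at the 30 cut.

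**The case against.** The strongest reply is that the plan specifies almost nothing about the GEE, so any error rate belongs to a model supplied by the reader. A three-category ordinal GEE is a natural reading and was not fitted here. That stands: the percentages describe plausible ordinary implementations, not the plan itself. It does not remove the point, because binary logistic GEE on the scheduled visits is a routine implementation and the plan contains no safeguard.

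A reader might infer that having only two or three changers is what pushes false positives to about 15%. The documents do not support that. They give no within-patient variability, so the number of changers is an assumption. In a week-6 comparison, that few changers makes the test conservative (step 4). Inflation appears mainly when several visits per period are modelled at the rarer 30 mg/g cut. A figure near 15% belongs to that one setting with SD 0.5 and is not a general rate.

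It is also fair that the plan promises estimates and intervals rather than a decision rule, that albuminuria is secondary, that Potential Pitfalls calls the study exploratory, and that continuous analyses are already planned. These limit the consequence. They do not make the interval valid, since it comes from the same standard error as the Wald test.

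**Conclusion.** The concern holds in a bounded form. GEE on albuminuria category with 18–19 patients and no small-sample method can give invalid errors or no estimate. With weeks 4 and 6 modelled, false positives are roughly 9–17% of usable fits at the 30 mg/g cut and about 4–10% at 300, and up to about a fifth of fits fail at 30. With week 6 alone the rate is about 1–7%, and the trouble is failed fits (up to about half) and very low power.

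These figures assume a lognormal ratio fitted to the 73-patient cohort, the within-patient SDs stated above, a two-sided 5% test, and no treatment, period or carry-over effect. Simulation error is about 1–2 percentage points. It would be too strong to conclude that the trial's main result is at risk: the primary endpoint is FMD and is unaffected.

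**What to change.** Name the continuous linear mixed model as the basis for inference on albuminuria. Report category as a normo/micro/macro shift table by treatment at week 6, either descriptively or with an exact within-patient test. State in advance which test: exact McNemar, or Mainland–Gart if stratification by sequence is wanted.

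If GEE is kept, prespecify the cut, visits, link and working correlation, use a small-sample-corrected variance such as Mancl–DeRouen with a t reference on n − 2 df, say what is done if the model does not fit, and do not use it at the 30 mg/g cut.

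The cost is SAP wording only. The downside is that the categorical test will rarely be significant: it needs at least 6 or 7 discordant patients, where fewer than about 4 are expected at either cut. A week-6 table also sets aside the week-4 category data.
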